#### 7.6.4 Marker cluster placement

Each segment is defined using a minimum of 3 cluster based markers which are not collinear. A range of marker clusters (marker diameter 14mm) will be used depending on the anthropometric characteristics of the participant e.g. size, arm length and width in addition to ensuring adequate visibility of markers. A description of the marker cluster placement has been described below and has been adapted from Jaspers et al 2011.

As a quality control measure, **the borders of all clusters** will be marked to ensure no movement has occurred.

Placement illustration	Description of placement
	
1. Sternal marker cluster
 
Positioned using double sided tape on the anterior aspect of the thorax, approximately one finger width below the sternal notch. Placement must be below the sterno-clavicular joint and in keeping with the midline of the body. The antero-superior border of the thorax is defined by the insicura jugularis (IJ) point and the antero-inferior border is defined Processes Xiphoideus (PX) point.
 
For participants with breast tissue, a more superior placement of the sternal cluster may be required, not exceeding the antero-superior border of the thorax. In this case, adequate visibility of the marker cluster should be ensured prior to identification of virtual markers.
 
Mark the inferior edge of the cluster.

	
2. Acromion marker cluster
 
Positioned using double sided tape on the flat surface of the acromion. Secure to the acromion with extra tape.
 
Following identification of the acromioclavicular joint, palpate posteriorly to identify the flattest area of the acromion.
 
Mark the base of the cluster.

	
3. Humeral marker cluster
 
Positioned using velcro on the distal aspect of the humeral segment. As a general guide the inferior component of the marker cluster should be proximal to and in line with the lateral epicondyle (LE) of the humerus.
 
Mark the inferior edge of the cluster.

	
4. Forearm marker cluster
 
Positioned using velcro on the postero-distal aspect of the forearm segment.
 
As a general guide the inferior border of the marker cluster should be proximal to the radial styloid (RS) and ulnar styloid (US) points.
 
Mark the inferior edge of the cluster.

	
5. Hand marker cluster
 
Positioned using double sided tape on the dorsal aspect of the hand. The marker cluster should be placed distal to the 3rd carpometacarpal joint and distal to all row of metacarpophalangeal joints.
 
The cluster is shaped like a V and the centre of the cluster should align with the 3rd metacarpal head.
 
Mark the inferior edge of the cluster.

[figure not shown]
### 7.6.5 Virtual marker identification and static calibration

Following completion of the sEMG placement, the virtual markers will be identified using a pointer. This requires placement of the pointer tip on the bony landmarks outline in section 7.6.2. This is completed with the participant in sitting with their hand on their knee. The virtual markers and movements required for calibration are:

No.	Name	Abbreviation	Checklist
1.	C7 Spinous Process	C7	
2.	T8 Spinous Process	T8	
3.	Insicura Jungularis - (Jugular notch)	IJ	
4.	Processus Xiphoideus - (Xiphisternum)	PX	
5.	Art. Sternoclavicularis – (Sternoclavicular joint)	SC	
6.	Art. Acromioclavicularis - Acromioclavicular joint	AC	
7.	Processus Coracoideus - Coracoid process	PC	
8.	Trigonum Scapulae – medial border spine of scapula	TS	
9.	Angulus Inferior (AI) - inferior angle of the scapula	AI	
10.	Angulus Acromialis - Latero-inferior edge of scapula spine	AA	
11.	Glenohumeral rotation center*	GH	
12.	Lateral epicondyle	LE	
13.	Medial epicondyle	ME	
14.	Radial Styloid	RS	
15.	Ulnar Styloid	US	
16.	Styloid process of 3 rd Metacarpal	MC3	
17.	Distal head of 2 nd Metacarpophalangeal joint	MCP2	
18.	Distal head of 3 rd Metacarpophalangeal joint	MCP3	
19.	Distal head of 5 th Metacarpophalangeal joint	MCP5	
20.	Hand on knee – static for trial and sEMG**	HandKnee	

\* Calculated via regression – with the participant's arm in abduction ask them to rotate their arm in a circular motion.

\*\* Participant seated with their hand on their knee and their contralateral hand holding the pointer as per the image.

## 7.7 Movements for data capture

### 7.7.1 Grip Strength

Participants will have their grip strength tested using a handheld dynamometer. The total repetitions **will not exceed 3** for each activity and will be broken up into **3 sets of 1 repetition each side**.

- **Testing limb**
  - affected and unaffected arm [children with instability]
  - left and right/ dominant and non-dominant arm [children without instability]
- **Starting position** – Participant in standing. Elbow flexed to 90° with hand in thumbs up position with handheld dynamometer.
- **Movement task** – Participants will be instructed to squeeze the handheld dynamometer as hard as they comfortably can for no longer than 5 seconds

### 7.7.2 Physiological movements

- For *Physiological movements* and *Functional tasks* – the total number **will not exceed 12 repetitions** for each activity in total and will be broken up into **2 sets of 6 repetitions**.
- For the *Movements under load* – the total number **will not exceed 6 repetitions** for each activity in total and will be broken up into **2 sets of 3 repetitions**.

Before each movement activity, participants will have the required movements demonstrated to them along with instructions regarding the start and finish positions.

### P1. Flexion

- **Testing limb**
  - affected arm [children with instability]
  - dominant [children without instability]
- **Starting position** – Participant in standing. Palmar surface resting on the lateral aspect of their thigh (in keeping with the midline of the body in the coronal plane).
- **Movement task** – Participants will be instructed to lift their arm out in front of them as high as they possibly can and then return it to the starting position.

## **P2. ABduction**

- **Testing limb**
  - affected arm [children with instability]
  - dominant [children without instability]
- **Starting position** – Participant in standing. Anatomical position i.e. Lateral aspect of the hypothenar eminence resting on the lateral aspect of their thigh (in keeping with the midline of the body in the coronal plane).
- **Movement task** – Participants will be instructed to lift their arm out to their side as high as they possibly can and then return it to the starting position.

## **P3. Abduction to $\approx 45^\circ$ and then lateral rotation**

- **Testing limb**
  - Affected arm [children with instability]
  - dominant [children without instability]
- **Starting position** – Participant in standing. Elbow flexed to  $90^\circ$  with hand in thumbs up position.
- **Movement task** – Participants will be instructed to lift their arm out to their side up to  $\approx 45^\circ$  at the shoulder. Maintaining the arm in this position, participants will then be asked to laterally rotate their shoulder as far as is comfortable for the required or maximally tolerable amount of repetitions. Following this, participants will be instructed to then return it to the starting position.

### **7.7.3 Functional tasks**

#### **F1. Hand behind head**

- **Testing limb**
  - affected arm [children with instability]
  - dominant [children without instability]
- **Starting position** – Participant in standing. Palmar surface resting on the lateral aspect of their thigh (in keeping with the midline of the body in the coronal plane).
- **Movement task** – Participants will be instructed to place their hand on the top of their head and then return it to the starting position.

#### 7.7.4 Movement under load

- **These will not exceed 6 repetitions for each i.e. 2 sets of 3 repetitions**

Participants will perform the movements outlined below under a loaded condition using a self-selected weight. The participants will be provided with a series of weights from which to choose and advised to select a weight that allows them to complete the movements comfortably.

#### M1. Flexion

- **Testing limb**
  - affected arm [children with instability]
  - dominant [children without instability]
- **Starting position** – Participant in standing with weight in hand. Palmar surface facing the lateral aspect of their thigh (in keeping with the midline of the body in the coronal plane).
- **Movement task** – Participants will be instructed to lift their arm out in front of them as high as they possibly can and then return it to the starting position.

#### M2. Abduction

- **Testing limb**
  - affected arm [children with instability]
  - dominant [children without instability]
- **Starting position** – Participant in standing with weight in hand. Anatomical position i.e. Lateral aspect of the hypothenar eminence facing the lateral aspect of their thigh (in keeping with the midline of the body in the coronal plane).
- **Movement task** – Participants will be instructed to lift their arm out to their side as high as they possibly can and then return it to the starting position.

#### M3. Abduction to $\approx 45^\circ$ and then lateral rotation

- **Testing limb**
  - affected arm [children with instability]
  - dominant [children without instability]
- **Starting position** – Participant in standing. Elbow flexed to  $90^\circ$  with hand in thumbs up position.
- **Movement task** – Participants will be instructed to lift their arm out to their side up to  $\approx 45^\circ$  at the shoulder. Maintaining the arm in this position, participants will then be asked to laterally rotate their shoulder as far as is comfortable for the required or maximally tolerable amount of repetitions. Following this, participants will be instructed to then return it to the starting position.

## **7.8 Follow up for recurrent instability**

Following the movement analysis session, participants will be provided with a diary to record and further episodes of instability as per (appendix). Provided with information and guidance on how to complete the diary. Participants in both groups will additionally be followed up on a monthly basis via a telephone call for up to 12 months to record the number of instability episodes experienced. Monthly follow ups have been selected to ensure accurate recording of instability episodes and facilitation of diary recordings.

## **7.9 Withdrawal criteria**

Participants' have a right for unrestricted withdrawal at any point of this study. Participants have been informed within the information sheet that if they choose to withdraw, identifiable data already collected with consent would be retained and used in the study. No further data would be collected or any other research procedures carried out on or in relation to the participant. Participants have also been instructed that if they wish to withdraw they may do so and no one will mind.

## 8 STATISTICS AND DATA ANALYSIS

### 8.1 Sample size calculation

This is an observational, cross-sectional study.

- A power calculation, used to determine the required sample size, is not possible for this study as the standard error of measurement (SEM - essential to identify a minimally clinically important difference) is not known.
- This study will provide the data from which SEM can be estimated and this can then be used to inform power calculations for future studies.
- Our rationale for selecting a sample size of 15 in each group (30 total) has been based on previous work which has developed and then implemented protocols for clinical practice.
- The two references cited below have developed clinical measurement protocols using sample sizes of 10 typically developing children and 12 children with cerebral palsy affecting the upper limbs.
- In the absence of an equivalent study in paediatric shoulder instability a sample size of 15/group reflects the current research practice in the literature and will be able to provide us with population estimates of “standard error of measurement - SEM” in typically developing children and those with upper limb pathology.

Jaspers, E., et al., Upper limb kinematics: development and reliability of a clinical protocol for children. *Gait Posture*, 2011. 33(2): p. 279-85.

Jaspers, E., et al., The reliability of upper limb kinematics in children with hemiplegic cerebral palsy. *Gait & Posture*, 2011. 33(4): p. 568-575.

### 8.2 Planned recruitment rate

Investigation of referral patterns with clinical collaborators prior to covid-19 (ORLAU, RJAH, Oswestry) demonstrated that clinical recruitment is realistic and achievable. There are approximately 2 referrals a month for children with instability who meet our inclusion criteria. Risk mitigation against under recruitment will be achieved by additionally advertising the study in clinical centres in the West Midlands such as specialist clinics, GP services and primary care settings, where practitioners will signpost potential participants to the primary organisation. Posters with information regarding the study will also be located in the respective departments. We will also advertise the study through social media using an electronic version of the poster.

### 8.3 Statistical analysis plan

The aim of this study is to identify factors responsible for recurrent shoulder instability in children. To meet the main aim, the following objectives, need to be met. The methods of analysis used to meet the study objectives have been reported below.

The analysis of measurement units will inform the main study objective and secondary objectives.

- **Kinematic** data such as joint angles and displacements – average range of movement values, as well as absolute minimum and maximum values will be reported for all functional tasks. For comparison purposes, descriptive statistics will be used to report the group behaviours and variability including means and standard deviations.
- **Kinetics** - force/strength – The range of force and strength values, as well as absolute minimum and maximum values will be reported for all functional tasks. For comparison purposes, descriptive statistics will be used to report the group behaviours and variability
- **Muscle activity patterns** - muscle activity (absence or presence), timing of muscle onset, percentage of maximum contraction and time of peak intensity will be used. This methodology is consistent with previously published research and is used for informing clinical decision making processes

The secondary research objectives used to address the main aim of the study are:

1. Validation of a 3D movement analysis protocol for measuring upper limb function in children with shoulder instability.
  - i) Individual variability (associated with of the measurement units outlined above) will be determined using the coefficient of variation for all data.
  - ii) The reliability and error associated with the protocol will be determined using the standard error of measurement for the measurement units outlined above. The reliability of the protocol will be determined through a sensitivity analysis investigating what effect perturbation of the virtual markers has on the outputs of the biomechanical model e.g. kinematics, position of the humerus
2. Obtain new data on muscle activity and movement patterns of children with and without shoulder instability
  - i) The method of analysis outlined above will inform this objective
3. Categorising clinical presentations of instability and identification of important factors for recurrent instability
  - i) data from study objective 2 will be evaluated to identify features i.e. movement or muscle activity patterns, which may be used to categorise clinical presentations of shoulder instability. An appropriate clustering/categorisation method will be selected once the characteristics of the dataset has been established

if we get a large enough sample size of participants with a homogenous clinical presentation and if three or more groups are identified in the preceding work package, an analysis of variance (ANOVA) can be used. For less than three groups, an independent sample t-test will be used.

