#### 3.2 Secondary Objectives

The secondary research objectives used to address the main aim of the study are:

- Validation of a 3D movement analysis protocol for measuring upper limb function in children with shoulder instability.
- Obtain new data on muscle activity and movement patterns of children with and without shoulder instability
- Categorising clinical presentations of instability and identification of important factors for recurrent instability

This is not an experimental study and so there is not a single/primary outcome measure. The following outcomes will be derived from this study

*For the single movement analysis session:*

- **Kinematic** variables related to the movement tasks, for example
  - joint angles (degrees)
  - displacement (position, speed and associated derivatives)
- **Kinetic** variables related to the movement tasks, for example
  - forces/ strength (n, kg/force)
- **Muscle activity patterns** related to the movement tasks, for example
  - Surface electromyography (sEMG) (mv)

*For the follow up outcomes:*

- Number of recurrent episodes of instability

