#### **4 STUDY DESIGN**

This is an observational, cross-sectional study of children (aged 8 to 18) presenting with shoulder instability of any origin, traumatic or atraumatic (n=15) and an age-matched sample (n=15) with no history of shoulder problems. Muscle activity and movement pattern differences will be measured using non-invasive 3D motion capture and surface electromyography, to identify factors responsible for instability. Only a single visit to the site will be required (ORLAU, RJAH). No interventions or treatments are included in this study as this is an observational, cross-sectional study.

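### Section 8.3 summarises kinematics only by range, minimum and maximum, which cannot show coordination in the maximal lifts, and it leaves displacement and speed unscaled for arm length across ages 8 to 18

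*Combined protocol and SAP*

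**What the plan says.** Section 4 (Study design) states the question: "Muscle activity and movement pattern differences will be measured using non-invasive 3D motion capture and surface electromyography".

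Section 3.2 lists the kinematic outcomes, by way of example, as joint angles and "displacement (position, speed and associated derivatives".

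Section 8.3 takes kinematic "data such as joint angles and displacements" and says that "average range of movement values, as well as absolute minimum and maximum values will be reported for all functional tasks". For comparison, "descriptive statistics will be used to report the group behaviours and variability including means and standard deviations". Speed and derivatives get no summary of their own.

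For secondary objective 2 (new data on patterns) section 8.3 adds only: "The method of analysis outlined above will inform this objective". For objective 3 (categorising presentations), "data from study objective 2 will be evaluated to identify features i.e. movement or muscle activity patterns". The clustering method is left until the data have been characterised. An independent-samples t-test is kept for fewer than three groups.

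The tasks in section 7.7 are of three kinds:

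- P1, P2, M1 and M2 are maximal lifts. In P1 the child is told to "lift their arm out in front of them as high as they possibly can".
- P3 and M3 hold abduction at about 45 degrees and then rotate.
- F1 moves to a fixed target. It is the only task listed under section 7.7.3, Functional tasks.

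Body size is mentioned in section 7.6.4, for choosing marker clusters. No section gives an angle at a matched elevation, a time-normalised curve, an inter-segment coordination measure, a kinematic timing measure, or scaling by limb length.

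**The concern.** A movement pattern is the way scapula, humerus and trunk move relative to one another during the task. The planned summaries describe the ends of each angle's path and not the path itself.

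In a maximal lift, a child who moves in the usual way but stops earlier shows a lower scapular maximum than one who lifts fully. A child with different coordination who reaches the same endpoints shows no difference at all. Objective 2 adds no further method and objective 3 draws on objective 2's data, so the gap carries through to the categorisation. It also reaches objective 1: the standard error of measurement is to be computed for these same measures, and section 8.1 intends it for future power calculations. Reliability would then be known only for amplitudes.

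The second issue is scale. Linear displacement and speed are larger in a longer arm for the same joint motion. Over ages 8 to 18 this adds spread unrelated to instability, both to the group standard deviations and to any clustering that uses raw displacements.

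**Working it through.** The documents state no effect size, standard deviation, alpha or power, so there is no planned figure to reproduce. All inputs below are assumptions, except 15 per group (section 8.1) and ages 8 to 18 (section 6).

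**1. Same extremes, different coordination.** Let elevation run from 0 to 150 degrees, with s the fraction completed. Take three scapular curves: 50s (even), 50s³ (late) and 50[1 − (1 − s)³] (early). Glenohumeral angle = 150s − scapular angle. In all three the scapular minimum, maximum and range are 0, 50 and 50, and the glenohumeral ones are 0, 100 and 100. At s = 0.5, which is 75 degrees of elevation:

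| Curve | Scapular | Glenohumeral | Ratio |
|---|---|---|---|
| Even | 25 | 50 | 2.0 |
| Late | 6.25 | 68.75 | 11.0 |
| Early | 43.75 | 31.25 | 0.71 |

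The planned summaries are identical for the three. This needs no assumption about real children; it shows only what range, minimum and maximum can and cannot carry.

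**2. Lift height.** Suppose the scapula supplies 25 to 40% of elevation in both groups and cases stop 20 to 40 degrees lower. The maximum scapular rotation then differs by 0.25 × 20 = 5 to 0.40 × 40 = 16 degrees with the same pattern, and by 0 at a matched elevation.

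**3. Arm length.** Vertical hand excursion with a straight arm is L(1 − cos θ). At θ = 155 degrees, 1 − cos θ = 1.906:

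- L = 50 cm gives 95.3 cm and L = 75 cm gives 143.0 cm, a ratio of 1.50 at the same joint angle. Over the other ranges tried the ratio is 70/55 = 1.27 and 80/45 = 1.78.
- A child at the mid-length of 62.5 cm who stops 12 degrees lower (143 degrees, 1 − cos θ = 1.799) loses 62.5 × (1.9063 − 1.7986) = 6.7 cm. The size effect is 143.0 − 95.3 = 47.7 cm.

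**4. Effect on a group comparison.** With 15 per group, two-sided alpha 0.05 and 80% power, the detectable standardised difference is (1.960 + 0.842) × √(2/15) = 1.02 (1.06 by the t distribution). Set a true difference of 1.02 SD in peak angle, with L uniform on 50 to 75 cm and an SD of peak elevation of 12 degrees. Brackets give the range over 55–70 to 45–80 cm and SDs of 8 to 16 degrees.

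| Measure | Standardised difference | Power |
|---|---|---|
| Peak angle | 1.02 | 77% |
| Raw displacement | 0.45 (0.22–0.75) | 22% (9–51%) |
| Displacement ÷ arm length | 0.98 (0.96–1.00) | 74% (72–75%) |

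Arm length explains about 85% of the variance in raw displacement (52 to 96%).

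**5. Effect on categorisation.** Simulate 15 cases with ages uniform on 8 to 18, arm length rising from 50 to 75 cm, six displacement features with 8% noise, and two-group k-means. Agreement with the younger/older split is about 88% on raw values and about 61% after removing arm length, which is roughly the chance level. The result depends on the set-up:

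- 15% noise with arms of 55 to 70 cm: 73% on raw values.
- 25% noise with arms of 55 to 70 cm: 65%.
- Six added size-free features carrying a real two-group difference of 2 SD: about 80%.
- Twelve such features: about 62%, no better than chance.
- Twelve added features with no real groups: about 85%.

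**The case against.** Several points on the other side stand.

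- **Angles do not scale with size.** A reader might infer that all the kinematics are confounded by body size. Only linear displacement, speed and derivatives are.
- **Lift height matters in four of seven tasks.** F1 has a fixed target and P3 and M3 hold abduction near 45 degrees. Even in the lifts, extremes carry some information on pattern.
- **Nothing is excluded.** The kinematic variables are given as examples, so a reader who infers that section 8.3 rules out pattern measures or scaling goes too far. It fails to specify them.
- **Muscle timing is planned.** Onset, presence or absence, percentage of maximum contraction and time of peak are pattern measures. They do not describe how the segments move together.
- **Controls are age matched and the kinematic comparison is descriptive.** Matching limits size bias between the groups. It does not remove size from the standard deviations, from an unpaired t-test, or from clustering within cases.
- **Raw displacements as clustering inputs are an inference.** Objective 3 draws on objective 2's data but does not name the features. That the categories would split by body size is therefore not supported; they could, if raw displacements dominate the feature set.
- **No document says cases lift less.** Assessment is at least 12 weeks after the last episode. The 5 to 16 degree figure rests wholly on an assumed shortfall and an assumed scapular share.

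**Conclusion.** The point holds as a gap between question and summary measure. For P1, P2, M1 and M2, range, minimum and maximum cannot distinguish different scapular-humeral coordination with the same endpoints, and they depend partly on lift height. The first of these follows by construction and needs no assumed data.

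The scale problem is confined to linear measures. Its direction is certain, since a longer arm gives a larger displacement at the same angle. Its size is not known from the documents: the fall from 1.02 to 0.45 SD (0.22 to 0.75) and the 88% agreement with age rest on assumed arm lengths, angle spread and noise, and should be read as illustrations.

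A separate ambiguity affects the same sentence. Read literally, its scope is the tasks under section 7.7.3, which is F1 alone, so it is unclear whether P1–P3 and M1–M3 are summarised at all.

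The plan should be changed, but the study is not invalidated. The motion data are recorded whichever summaries are chosen.

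**What to change.** In section 8.3:

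1. Keep range, minimum and maximum, with maximum elevation as its own outcome. For P1, P2, M1 and M2 add scapular, glenohumeral and trunk angles at set humerus-to-thorax elevations, for example 30, 60, 90 and 120 degrees where reached, with raising and lowering reported separately. Time-normalised curves or a coordination ratio would be acceptable alternatives if named in advance. Set elevations do not suit P3 and M3, where elevation is held.
2. Divide linear displacement, speed and derivatives by arm length before any group comparison or clustering. Arm length can be the sum of segment lengths from landmarks already digitised in section 7.6.5 (AC, LE, US, MCP3).
3. State that the summaries cover P1–P3 and M1–M3 as well as F1.

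The cost is SAP wording and some scripting, with no extra visit, task or measurement. The drawback is that children who do not reach the higher elevations contribute only to the lower ones, so the number contributing at each elevation should be reported.

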### **Measurement burden**

In order to minimise the measurement burden on all participants and ensure the aims of the study are met, our study design has been developed following input from a Public Involvement and Engagement

(PPIE) group, an additional 7 children of appropriate age groups outside of the PPIE and clinicians who routinely work with children with shoulder instability.

A primary aim of our study is to test the reliability and variability of a measurement analysis protocol in children with shoulder instability and age-matched controls. To minimize the measurement burden on children and their parent/carer/guardian, only a single study site visit, lasting a maximum of 2 hours 30 minutes, is required. Reliability will be determined by a sensitivity analysis in which we will virtually perturbate the markers post data collection. This has been selected to minimise the measurement burden of multiple visits for children with shoulder instability and the age matched controls. For children with shoulder instability this will also minimise the variability which may arise as a result of the natural recovery process over time and confound our results. The measurement protocol has been designed after consultation with different children of appropriate age groups, clinicians and the scientific literature.

Where possible, we will additionally try and accommodate measurement sessions outside of school hours for both groups to limit any school/lesson absences.

Diaries and monthly telephone calls (lasting up to 12 months), have been selected to ensure accurate recordings of the events and minimise recall bias. We have received input re the follow up study processes and diaries from the Public Involvement and Engagement group and additional children of appropriate age groups. We do not anticipate that participants will have a large number of instability episodes and so the measurement burden for recording will be minimal. Additionally, participants will only be asked to record when an episode happens.

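### Objective 1(i) applies the coefficient of variation to every variable, including muscle absence/presence, absolute angles and positions, and times with no stated origin, for which it is the wrong statistic

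*Combined protocol and SAP*

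**What the plan says.** Section 8.3 lists the measurement units and then sets the analysis for each secondary objective. For the first objective, validation of the movement protocol, part (i) reads: "Individual variability (associated with of the measurement units outlined above) will be determined using the coefficient of variation for all data". No variable type is exempted.

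The units it refers back to are:

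- **Kinematics.** Average range of movement for joint angles and displacements, and also "absolute minimum and maximum values will be reported for all functional tasks". Section 3.2 describes displacement as "displacement (position, speed and associated derivatives").
- **Kinetics.** Force and strength.
- **Muscle activity.** "muscle activity (absence or presence), timing of muscle onset, percentage of maximum contraction and time of peak intensity will be used". Neither section 8.3 nor any other section says from what event the times are measured.

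Part (ii) of the same objective adds a second statistic: "The reliability and error associated with the protocol will be determined using the standard error of measurement". Group means and SDs are also planned for kinematics.

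**The concern.** The CV can be interpreted when zero means none of the quantity and the mean is well above zero. Range of movement, speed, force/strength and percentage of maximum contraction have such a zero. Three other classes under the same rule do not fit:

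1. **Muscle absence/presence.** For 0/1 data the CV only re-expresses the proportion active. It changes with the state coded as 1, and it is undefined when the mean is zero.
2. **Absolute minimum and maximum angles and positions.** Their zero is set by the axis convention. Minima near or below zero are plausible where a task begins at rest; F1 starts with "Palmar surface resting on the lateral aspect of their thigh".
3. **Onset and peak times.** The CV depends on a time origin that the plan does not give, and it turns negative if mean activation precedes that origin.

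Any derivative that can be negative would have the same problem as class 2. Derivatives appear in section 3.2 but not in 8.3, and are not said to be signed.

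The CV is the only statistic named for individual variability, and the Measurement burden text treats the protocol's reliability and variability as a primary aim. Followed literally, the rule could make equally repeatable variables look very different, or leave values that cannot be reported.

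**Working it through.** The plan gives no CV, within-child SD or mean, so there is no figure to reproduce. The check works from the definition CV = SD/mean.

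**Inputs from the documents.** Up to 12 repetitions per unloaded task (section 7.7.2) and up to 6 under load (section 7.7.4).

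**Assumptions.** All angle, SD and time values are illustrative. Individual variability is read as variability between a child's repetitions, with absence/presence scored on each repetition.

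**(a) Absence/presence.** With the muscle active in k of n repetitions, the sample CV of 0/1 data is √[n(n−k) / (k(n−1))].

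| n | k | Calculation | CV |
|---|---|---|---|
| 12 | 1 | √(12×11 / (1×11)) | 346% |
| 12 | 11 | √(12×1 / (11×11)) | 31% |
| 6 | 1 | √(6×5 / (1×5)) | 245% |
| 6 | 5 | √(6×1 / (5×5)) | 49% |
| any | 0 | 0/0 | undefined |

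Within each n, the two patterns have the same agreement (11 of 12, or 5 of 6). Coding absence as 1 swaps their CVs. The SD does not change with the coding (0.289 for both k = 1 and k = 11 at n = 12).

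**(b) Angles.** 200,000 simulated children per case, normal repetitions, within-child SD 3 degrees, 12 repetitions:

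| True mean (degrees) | CV, 5th to 95th percentile |
|---|---|
| −5 | −92% to −36% |
| 2 | 70% to 460% |
| 5 | 36% to 93% |
| 10 | 19% to 42% |
| 20 | 10% to 20% |
| 60 | 3.2% to 6.7% |
| 120 | 1.6% to 3.3% |

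The sample SD lies between 1.9 and 4.0 degrees in every row, because the repeatability is the same throughout.

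With the SD raised to 5 degrees the pattern is the same: 55% to 198% at mean 5, 16% to 34% at mean 20, and 2.3% to 4.8% at mean 140.

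The chance of a negative CV at a true mean of 2 degrees is Φ(−2√n / SD):

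- n = 12, SD 3: Φ(−2.31) = about 1%
- n = 6, SD 2: Φ(−2.45) = 0.7%
- n = 6, SD 3: Φ(−1.63) = 5.1%
- n = 6, SD 5: Φ(−0.98) = 16%

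The zero convention matters even for large angles. An SD of 3 at mean 120 gives 3/120 = 2.5%. With the zero moved by 90 degrees, the same movement gives 3/30 = 10%.

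**(c) Times.** With an SD of 30 ms, an onset averaging 20 ms after the origin gives 30/20 = 150%. Moving the origin 1 s earlier gives 30/1020 = 2.9%. Activation averaging 40 ms before the origin, with an SD of 50 ms, gives 50/(−40) = −125%.

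**The case against.** **The SEM in 1(ii) may already do the job.** It covers the same units and is an absolute error in original units. If computed from repetitions, it would be close to the within-child SD. This is a possible partial mitigation for continuous variables only. Part (ii) assigns the SEM to protocol reliability and error without giving its computation, and the Measurement burden text says: "Reliability will be determined by a sensitivity analysis in which we will virtually perturbate the markers post data collection". Marker perturbation does not measure how a child varies between repetitions, and an SEM does not suit absence/presence. The planned group SDs do not describe within-child variability either.

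**The minimum and maximum may be descriptive extremes only, and only for functional tasks.** Section 7.7.3 lists just F1 under that heading. On a literal reading the loaded-task angle figures fall outside the sentence. F1 remains inside it and starts at rest, and part (i) refers back to all the listed units without exception.

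**The striking angle figures need means of a few degrees.** This is correct. No joint angle or axis convention is given, and a hand at the thigh does not put every angle near zero. From about 20 degrees upward the CV is numerically well behaved, but it still depends on the convention.

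**Absence/presence might be judged once per muscle and task.** The plan does not say. Scoring by repetition is the natural reading of individual variability, and the 346% and 31% figures rest on it. With a single judgement there would be no within-child CV at all.

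**The missing time origin is a definition gap whatever the statistic.** This is true, but an SD is unchanged by a fixed shift of origin and a CV is not.

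**Minimum force and low percentage contraction can also be near zero.** This stands as a caution: their CV can be unstable too. Their zero is real, however, so the CV does not depend on a convention.

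**Nothing inferential uses the CV.** This is accepted. In section 8.1 it is the SEM, not the CV, of which the plan says "this can then be used to inform power calculations for future studies".

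**Conclusion.** The concern holds. The fault lies in applying the CV to all data, not in the CV itself. For absence/presence the result is exact once repetitions are scored: equal consistency gives 346% or 31% over 12 repetitions depending on coding, and no value if the muscle is never active. For absolute angles, positions and times, dependence on the chosen zero or origin follows from the definition and needs no assumed values; the percentages shown are illustrations. Severe instability or negative values arise only where means are near or below zero, while large maxima give stable but convention-dependent values.

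The effect is limited to the descriptive results of objective 1(i). It should be corrected before analysis, because choosing exceptions after seeing undefined or negative values would be a data-driven decision.

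**What to change.** Replace the single rule in objective 1(i) with a short list by variable type:

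- **Absolute angles, positions, any signed derivatives, and onset and peak times:** within-child SD across repetitions, in original units. State the time origin.
- **Range of movement, speed, force/strength and percentage of maximum contraction:** CV, with this set fixed in advance by variable type and not after looking at the means. Showing the SD beside it would expose any case where the mean is small.
- **Muscle absence/presence:** proportion of repetitions active, or percent agreement across repetitions. State that scoring is per repetition.

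The cost is one SAP paragraph and a definition of the time origin, with no new data or visits. The loss is that variability is no longer on one unit-free scale across all variables.
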